The proposed research will run a Parallel-Group Randomized Controlled Trial, employing an exploratory parallel-group randomized controlled trial study design and utilizing a multi-method and multi-source assessment protocol. a. The study is currently planned to take place at The Children's School at [name] b. We will use a repeated-measure within-subject design, gathering measurement of main outcomes at three time points to assess the efficacy of AAI for children with ADHD who are participating in a short-term intervention with or without the assistance of therapy dogs. A linear, repeated measures design will be utilized for our primary, and exploratory main outcome. c. Over the course of about 4 months, children will participate in treatment and assessment for a total up to approximately 16-20 hours) and parents will participate in approximately 6-9 hours of assessment. d. Children and their parents will first attend a screening visit that will last 2-3 hours to determine eligibility. e. If eligible, participation will require participants to attend group sessions for integrative, non-medical treatments for ADHD, once weekly (one weekday after school to be determined as space permits for about 2 hours per session (for a total of about 16-20 hours). These play group sessions may or may not include the participation of up to 3-4 certified therapy dog/handler dyads. These group sessions will be video recorded to capture child-child, child-dog, and dog behavior. f. Participation will also require child participants to attend three (3) Saturday "Laboratory School" assessment visits, immediately prior to and after the intervention period and then five weeks later. Each of these assessments will last approximately five to six (5-6) hours (about 18 total hours over three visits) for child participants and up to 2 hours each of three visits for parents (about 6 hours total). "Laboratory School" recess sessions will be video taped to capture observed child-child interactions. g. Participants will also be requested to wear a device used to collect heart rate (FirstBeat monitor) during the assessment days (3) and intervention sessions (3) and on the night prior to participation in the three (3) Saturday "Laboratory School" assessment visits. The FirstBeat monitors which have been found to be acceptable, feasible, safe and reliable for collection in several youth samples. For heartrate collection, parents will be instructed on how to affix a

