Statistical Method per Outcome Specific Aim 1: Replicate Previous Favorable Behavioral Response to AAI Primary Main Outcome: Behavior responses. This parallel-group randomized design and will utilize a multi-method and multi-source assessment protocol. The assessment protocol will use a repeated-measure within-subject design, gathering main outcomes at three time points to assess the efficacy of AAI on outcomes for children with ADHD who are participating in a short-term intervention with or without the assistance of certified therapy dogs (see Figure 1). Our previous research indicated that after just 2 weeks of intervention, participants in the AAI condition showed significantly greater improvement in symptoms compared to control participants and that these gains were maximized by 10 weeks and then maintained at 6 weeks post intervention ([name] et al., 2018a), suggesting that 10 weeks is an ideal duration of treatment to detect significant benefits from AAI with dogs. Outcomes from AAI utilizing a manualized treatment with therapy dogs (AAI) will be compared to standard of care evidence-based psychosocial treatment at usual (control). Specific Aim 2: Determine Physiological Response over time to AAI for children with ADHD. Exploratory Main Outcome: Diurnal HPA and ANS responses. To determine if children with ADHD present with measurable changes in physiological responses to a short-term AAI (10 weeks) on measures of HPA and ANS we will gather candidate salivary analytes (salivary cortisol, uric acid, and alpha-amylase; Cort, sUA, sAA, respectively) and measures of cardiac rhythm, (heart rate variability; HRV) prior to and post intervention for children participating in both treatment conditions before, immediately after, and upon treatment follow up. Specifically, for each domain we will ascertain changes in diurnal patterns of candidate physiological measures utilizing a linear, repeated measures design gathered across three (3) points in time; establishing individual baseline patterns, end of treatment patterns, and then patterns at 6 weeks post-treatment. Specific Aim 3; Explore Individual Differences as potential mediators of response to AAI in children with ADHD. Secondary Outcome Exploratory Mediator Analysis; In the proposed study, we will explore how children's individual (a) acute physiological responses during intervention sessions and their individual (b) social interaction quality during intervention sessions may play a role in each of the Main Outcomes. Specifically, we will a) ascertain acute HPA activity (as measured by Cort, and sUA) and acute ANS activity (as measured by HRV and sAA) during intervention sessions across

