
both treatment conditions and we will b) ascertain the quality of in-session social relationships (child-child) across both treatment conditions as well as the quality of in-session child animal interaction (child-dog) during the AAI sessions (observed child/child & child/dog interaction) at three (3) time points across the 10-week study intervention period (weeks 1, 5, & 10). The acute response and interaction quality measures from each of the three sessions will then be correlated with the degree of change in the primary main outcomes. (e.g., pre-post change in ADHD symptoms, social skills, regulation) and the exploratory main outcomes (e.g., pre-post change in diurnal HPA activity and ANS activity) to examine the potential mediation of individual differences on response to AAI with therapy dogs for children with ADHD. Here we provide an example of one mediation analysis for treatment group (AAI vs Control) as the primary predictor, salivary cortisol response slope at session 5 the potential mediator, and behavioral change (pre-post change) the outcome: First, cortisol response slope² means will be compared between the groups (the mediator must be related to the predictor). If significant, then the relationship between cortisol response slope², and behavioral change will be evaluated for a significant correlation/slope (the mediator must be related to the outcome). Finally a model will be run with both treatment group and cortisol response slope² predicting behavioral change. If the relationship between treatment group and behavioral change is reduced compared to the primary analysis (i.e., with treatment group alone), saliva cortisol response² is interpreted as providing a mediated effect. To obtain estimates of the size and significance of the indirect effects, bootstrapping procedures as described by Shrout and Bolger (2002) will be implemented. Due to the fact that bootstrapping procedures are still limited in the case of multilevel models, an approximation of the Sobel test will also be performed, along with Monte Carlo estimation of confidence intervals but because this aim is exploratory and this is not a fully powered study, results presented will include descriptive and confidence intervals.

Describe the statistical method(s) that will be used to analyze the primary outcome(s) or endpoints:

see previous section

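### In Aim 3, a week-10 in-session measure related to pre-post change cannot be told apart from a consequence of improvement, yet the plan would read it as mediation

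*Combined protocol and SAP*

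**What the plan says.** **Mediators.** Under Statistical Considerations, Specific Aim 3, acute physiology and interaction quality are recorded in session "at three (3) time points across the 10-week study intervention period (weeks 1, 5, & 10". Then "The acute response and interaction quality measures from each of the three sessions will then be correlated with the degree of change" in the main outcomes. The behavioural example of that change is "pre-post change in ADHD symptoms, social skills, regulation", and the physiological example is also pre-post. The stated purpose is to examine mediation.

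**Rule.** The worked example uses the session-5 cortisol slope. The groups are compared on the mediator. If they differ significantly, the mediator is tested against behavioural change. A joint model follows, and a reduced group effect is taken as mediation. Bootstrap, Sobel and Monte Carlo procedures are added for the indirect effect. The aim is called exploratory and not fully powered.

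**Outcome timing.** Study Design, item f, places the assessment visits "immediately prior to and after the intervention period and then five weeks later". Specific Aim 1 confirms the count: "gathering main outcomes at three time points to assess the efficacy of AAI".

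**Time course.** Also under Specific Aim 1, the prior study is summarised: "after just 2 weeks of intervention, participants in the AAI condition showed significantly greater improvement in symptoms compared to control participants", and "these gains were maximized by 10 weeks and then maintained at 6 weeks post intervention".

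**The concern.** A mediator has to act before the change it explains. Week 1 precedes nearly all of the pre-post interval, while week 10 closes it. A calmer cortisol response or better peer interaction in the last session may be a product of improvement already made. The plan treats all three sessions alike. It sets no time-order requirement, does not label week 10 separately, and does not adjust for improvement reached before the session.

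Because outcomes are measured only before treatment, after treatment and at follow-up, no later analysis can recover the order. The bootstrap, Sobel and Monte Carlo procedures describe sampling error in the indirect effect. They say nothing about its direction. Mechanism is the declared purpose of the study, and the results are meant to inform larger trials, so a finding with cause and effect reversed would be carried forward.

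**Working it through.** The plan gives no power or error figure for Aim 3, so there is none to reproduce. The timing argument rests on the passages quoted above; the simulation only illustrates its size.

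**Inputs from the documents.** 48 children in two groups (Sample Size); 24 per arm assumes equal allocation. Effects of .45 and .86 (Power & Expected Effect Size), read here as standardised differences d. Alpha .05 is stated for Aim 1; its two-sided use in Aim 3 is assumed.

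**Assumed, not in the documents.** A share f = .5 to .7 of change is made before week 10. The mediator correlates r = .3 to .5 with that early change.

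**Reverse-causation model.** With T = 0 or 1 for group and e, u, v independent standard normal:
- final change Y = d·T + e
- early change A = s·T + ρ·e + √(1−ρ²)·u
- mediator M = r·A + √(1−r²)·v

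M has no effect on Y, so every declared mediation is false. Early change is modelled in three ways:
1. ρ = f and s = f·d (f read as a correlation).
2. ρ = √f and s = √f·d (f read as a share of variance and of the group effect).
3. ρ = √f and s = d (early change already separates the groups by the full d, in its own SD units).

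The stepwise rule counts a trial when the group difference in M has p<.05, the M–Y correlation has p<.05, and the adjusted group effect is smaller. The interval is a 95% Monte Carlo interval for the indirect effect.

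**Results (6,000 trials per setting; lowest to highest over f, r and d):**

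| Model | Stepwise rule | Interval excludes 0 | Correlation p<.05 |
|---|---|---|---|
| 1 | 1–16% | 1–12% | 18–76% |
| 2 | 3–23% | 1–19% | 32–91% |
| 3 | 3–29% | 2–26% | 33–92% |

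The lowest stepwise corner came out at 1.4% here and 1.8% in a separate run of 2,000 trials, hence roughly 2–29% overall. The interval's top depends most on the model: 19% under model 2, and 20–26% under model 3 at d = .86 and r = .5. When M is unrelated to change (f = 0), the stepwise rule gives 0.2–0.9%.

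**Check by hand.** The first step limits the stepwise rate. The standard error of the group difference in M is √(2/24) = .289.
- Lowest corner (model 1, f = .5, r = .3, d = .45): expected difference .3 × .5 × .45 = .0675, and .0675/.289 = .23, so the first step is passed in about 6% of trials. The within-arm correlation is .3 × .5 = .15, against a critical value of about .285 at n = 48.
- Highest corner (model 3, f = .7, r = .5, d = .86): expected difference .5 × .86 = .43, and .43/.289 = 1.49, so the first step is passed in about 32%. Multiplying by the 92% correlation rate gives .32 × .92 ≈ .29, which matches the table.

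**The case against.** The case against has substance. The only fully specified mediation uses session 5. The outcomes are introduced as examples, so follow-up change is not excluded. The aim is exploratory, with descriptive results and intervals promised. All of this lowers the stakes. None of it supplies a time order: the three-session sentence brings week 10 in, no outcome other than pre-post change is specified, and an interval around a wrongly ordered effect still misleads.

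Three stronger readings are tempting, and the documents do not support them.
- **That the plan would claim false mediation as often as the bare correlation is significant, up to about 91%.** In the worked example the mediator must first differ between groups and the group effect must then shrink. The stepwise figures are the relevant ones, and at the low end they fall below 5%.
- **That improvement is largely complete before week 10 for every Aim 3 outcome.** The prior-study summary concerns symptoms and gives no proportion. No time course is given for social skills, regulation or the diurnal measures.
- **That the week-10 analyses are void.** Week 10 still precedes the post visit, and a late measurement may reflect a persisting individual difference. The result is ambiguous in direction, not meaningless.

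**Conclusion.** The concern holds in limited form. The plan applies one mediation reading to three occasions, and at week 10 the design cannot distinguish a mediator from a consequence of improvement. This follows from the visit timing and the absence of a mid-treatment outcome. It does not depend on the simulation.

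Its practical size is uncertain: roughly 2–29% false mediation by the stepwise rule, about 1–21% by the interval (26% at one corner), and about 18–91% for the correlation alone. These figures rest on assumed f and r, and they are not bounds. If all change precedes the session, r = .7 and d = .86, the stepwise rate reaches 54%, but that lies outside the range assumed here.

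Week 5 is not clean either, since a group difference in symptoms was reported by week 2. At f = .5 and r = .3 to .7, the separate run gave stepwise rates of 1.8–15.5%. No primary outcome, sample size or safety decision is affected. The change is worth making because Aim 3 carries the study's mechanistic claim.

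**What to change.** In Statistical Considerations, Specific Aim 3:
- Name week 1 as the key mediator occasion for pre-post change.
- Keep week 5 as secondary, with the caveat that some gain may precede it.
- Report week 10 against pre-post change as descriptive association only, not as mediation.
- Optionally relate week-10 measures to post-to-follow-up change, adjusted for the post score. Follow-up is already collected, and Aim 2 already models post-to-follow-up change. State that this may be uninformative if gains are simply maintained, as the prior study reported.

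The Specific Aims describe an 8–10 week intervention, while Aim 3 assumes a week-10 session. The two should be reconciled so that the last mediator occasion is defined.

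**Cost.** Wording only. The Progress Report says no data had been analysed at that renewal, so a change made from that position would still be prespecified. The price is one fewer mediator occasion for pre-post change. Week 1 may also be a weaker index of a response that develops over sessions.

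### The Aim 3 mediation example has no baseline term, so the mediator-outcome path may be confounded and can show false mediation or hide real mediation.

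*Combined protocol and SAP*

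**What the plan says.** The only mediation specification is in Statistical Considerations, under Specific Aim 3. It is introduced with "Here we provide an example of one mediation analysis".

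- **Mediator:** "salivary cortisol response slope at session 5 the potential mediator".
- **Outcome:** "behavioral change (pre-post change) the outcome". The same approach is to be used for "pre-post change in diurnal HPA activity and ANS activity".
- **Step 1:** compare mean cortisol response between arms, and go on only if the difference is significant.
- **Step 2:** the mediator-outcome relation "will be evaluated for a significant correlation/slope (the mediator must be related to the outcome").
- **Step 3:** "Finally a model will be run with both treatment group and cortisol response" slope as predictors of change. "If the relationship between treatment group and behavioral change is reduced compared to the primary analysis", the marker is read as a mediator.

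Bootstrap, an approximate Sobel test and Monte Carlo intervals are then applied to the indirect effect. Results are to be given as descriptives and confidence intervals "because this aim is exploratory and this is not a fully powered study".

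No baseline score or other covariate appears at any step, and no other section supplies one. The baseline t-tests, in the answer on secondary and post hoc analyses, compare the arms with each other. The within-subject and within-cohort correlation terms, under Power & Expected Effect Size, belong to the Aim 2 models.

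**The concern.** Randomisation protects the arm-to-mediator path. It does not protect the mediator-to-outcome path, because children are not randomised to their in-session physiology or interaction quality.

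Raw change depends on baseline: with similar pre and post SDs and a correlation below 1, children who start high tend to fall more. If in-session response also tracks baseline severity, that shared dependence enters the mediator coefficient when baseline is left out. If AAI also shifts the mediator, it carries into the indirect effect.

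The planned interval methods describe sampling error around whatever the model estimates, so they leave this bias in place. Mechanism is the stated purpose of the trial, and the findings are meant to inform larger multi-site trials. A wrong mediator, or a missed one, would carry forward.

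**Working it through.** **The plan's own figures.** No sample size, power or correlation is stated for Aim 3. The only stated figures the model uses are 52 enrolled and 48 analysed at about 8% attrition: 52 × 0.92 = 47.8, which agrees.

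**Inputs.**
- From the documents: n = 48 in two arms; type I error 0.05; earlier-trial effect of 0.45 on inattention (scale undefined, read here as SD units).
- Assumed, because the documents give no value: 24 per arm; two-sided tests; within-arm correlation r between baseline severity and the mediator; pre-post correlation ρ of 0.5-0.7; arm shift a in the mediator of 0.5-0.8 SD; true mediator effect zero. A negative arm effect means improvement.

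**Closed form.** Let X be baseline and T the arm, with X and the within-arm mediator scaled to SD 1:
- mediator = a·T + r·X + error
- post = ρ·X − 0.45·T + error
- outcome = post − X

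Within arm, cov(mediator, outcome) = r(ρ − 1). With X omitted, the mediator coefficient is therefore biased by r(ρ − 1), and the indirect effect by a·r(ρ − 1).

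| r | ρ | coefficient bias | indirect, a = 0.5 | indirect, a = 0.8 |
|---|---|---|---|---|
| 0.4 | 0.5 | −0.20 | −0.10 | −0.16 |
| 0.4 | 0.7 | −0.12 | −0.06 | −0.096 |
| 0.2 | 0.5 | −0.10 | −0.05 | −0.08 |
| 0.2 | 0.7 | −0.06 | −0.03 | −0.048 |

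At r = 0.4 the spurious indirect effect is 0.06-0.16 SD. That is 0.06/0.45 = 13% to 0.16/0.45 = 36% of the 0.45 effect.

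**Simulation of the same model** (2,000 trials per setting, a = 0.5-0.8, ρ = 0.5-0.7):

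| Setting | mediator test falsely significant | Monte Carlo interval excludes zero |
|---|---|---|
| r = 0.4, no baseline | about 18-28% | about 6-20% |
| r = 0.2, no baseline | about 7-11% | about 3-7% |
| observed baseline added | about 4-6% | about 2-5% |

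**Limits of the effect** (1,500 trials per setting):
- At r = 0.1, ρ = 0.5, a = 0.8, the rates without baseline are 6-7% and 5-6%, close to nominal.
- At r = −0.3, ρ = 0.5, a = 0.8, the bias reverses sign and opposes the AAI benefit. The literal three-step rule then declares mediation in only 2-3%. At r = +0.3 it does so in 24% (arm effect 0.45) or 41% (arm effect 0.86).
- At r = 0 that rule still declares mediation in 6% or 16%. This part comes from the rule, not from baseline: step 2 names no adjustment for arm, and step 3 accepts any reduction.
- If AAI does not move the mediator (r = 0.3, ρ = 0.6), the interval excludes zero in under 1%.

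**A different causal structure.** Suppose the mediator tracks only a stable trait, and the baseline score measures that trait with error (reliability 0.6-0.8, r = 0.3-0.5). Raw change is then unbiased, with 4-5% false positives. Adding observed baseline biases the coefficient by +0.06 to +0.18 and gives 9-30% false positives.

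For positive r, the change-score model errs negatively under the first structure and the adjusted model errs positively under the second. That is why agreement between the two is informative.

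**The case against.** The strongest case on the other side has four parts.

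1. **Direction.** The non-technical summary ties ADHD to under-arousal and proposes that dogs raise arousal. On that view severity lowers the mediator while AAI raises it, so the artefact works against the AAI benefit and step 3 is rarely met. This stands. The likelier error could be masking, which is still a wrong answer about mechanism.
2. **Regression to the mean.** A reader might infer that regression to the mean alone can yield a mediated effect. The documents do not support that: step 1 requires a significant arm difference in the mediator, and without an arm shift the interval almost never excludes zero.
3. **Remedy.** A reader might infer that raw change should be replaced by baseline adjustment. Under the stable-trait structure that replacement creates bias, and nothing in the documents settles which structure applies. In addition, acute response and interaction quality are first measured at week 1, so they have no pre-intervention value; child-dog interaction is seen only in AAI sessions.
4. **Scope.** The text is one example in an exploratory, underpowered aim reported with intervals. This limits the consequence. It does not remove the gap, because the example is the only specification given and it states when a marker is to be read as a mediator.

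**Conclusion.** The omission is clear in the text, and no other section fills it. Whether it distorts Aim 3 depends on three conditions that the documents do not quantify: in-session response is related to baseline severity, change depends on baseline, and AAI shifts the mediator. A reader might infer that baseline severity does confound the result and that false mediation follows. The supportable statement is that it may confound, in either direction.

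Under the assumed values the distortion is material at a baseline-mediator correlation of 0.4, modest at 0.2 and near nominal at 0.1. The closed form and the simulation agree. The point should be settled before Aim 3 is analysed, because it changes what that aim can conclude. The Aim 1 and Aim 2 comparisons do not depend on it.

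**What to change.** In each Aim 3 analysis:

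1. Add the child's baseline value of the outcome as a covariate in both the arm-to-mediator and mediator-to-outcome equations. Where one exists, also add the baseline diurnal level of the same marker.
2. Report this model beside the change-score model, and state in the plan that neither is unbiased under every causal structure.
3. Interpret a marker as a mediator only where the two models agree.
4. Report how the indirect effect moves under residual mediator-outcome correlations of 0.1-0.3 in either direction.

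The cost is a wording change, one or two model degrees of freedom and a second set of models. The baseline outcome and diurnal values come from the first Laboratory School assessment, so no new data are needed. The Progress Report states that no data had been analysed, so as of that report the change could still be made before results are seen.
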